5.3 Consent

Those eligible will be approached and provided with an information pack and consent form, which will be signed to indicate that informed consent has been given. Patients will be given ample time to consider taking part, more than 24 hours if they wish. The direct healthcare professional will first approach a patient about the study, and after verbal consent by the patient the healthcare professional themselves or a member of the research team can go through the informed consent process. If there is insufficient time in clinic, the podiatrist or delegated research can follow-up with a phone call to the patient to ensure they understand the PIS and have had opportunity to ask any questions they may have.

The start of the 4-week screening period is the date of written consent being obtained.

Participants will receive no incentives and consent will be regarded as a process and not a one-off event. Participants are free to withdraw from the study at any time without the need to give any reasons for withdrawal. Their standard of care will not be affected by either declining to participate in the study or withdrawing during participation. Data collected up to the date of withdrawal will be retained for analysis. Only one questionnaire will be presented to patients who withdraw or complete early, the patient experience questionnaire (still voluntary for patients to complete or not).

5.4 **Recruitment**

Participants will be enrolled for a total of 16 weeks, see Table 2, or until ulcer healing has been achieved (if the latter occurs then they will still be followed up according to the study schedule in terms of patient-reported outcome measures). All participants will have demographic and medical data obtained and a number of baseline and follow-up measures.

Table 2. Overview of study measurements

Weeks	-4	0*	3*	6*	9#	12~
Clinical characterization of wound	Х	Х	Χ	Х	Х	Χ
Ulcer size (Coloplast grid or suitable equiv)	Χ	Χ	Χ	Χ	Χ	Χ
PUSH score	Χ	Χ	Χ	Χ	Χ	Χ
SINBAD DFU grading score (DFU only)	Χ	Χ	Χ	Χ	Χ	Χ
Wound status (closed/recurrence/infection)		Χ	Χ	Χ	Χ	Χ
photo of wound (if possible and consented by patient)		Χ		Х		Х
QoL CWIQ		Χ		Χ		Х
QoL EQ-5D-5L		Χ		Х		Χ
Experience questionnaire (Natrox only)						Χ

^{*} Up to 1 week early or late

The Pressure Ulcer Scale for Healing (PUSH) tool is a standardised method of assessing and monitoring the severity and healing of both pressure ulcers and venous leg ulcers, and is also applied for foot ulcers (Stotts et al, 2001; Ratliff & Rodeheaver 2005). The Pressure Ulcer Scale for Healing (PUSH) is a valid, responsive, evaluative tool to monitor and document wound progress of foot ulcers (Hon, 2010). Findings also suggest that total PUSH scores predict time-to-heal for foot ulcers (Gardner 2011).

The SINBAD grading score was developed and validated for use in patients with diabetes (Ince etal, 2008).

5.5 **Follow-up**

Patients are in the study for a period of 16 weeks, of which 4 weeks are screening and 12 weeks are intervention or control. Thereafter, the patient will be followed up as they would be in normal clinical practice. During and after the trial, clinical staff will redress the wound as per routine care, and during the trial they will conduct the measurement of the foot ulcer (grid measurement tool, SINBAD grading and PUSH score). The researcher will be in attendance at week -4, 0, 3, 6, 9, and 12 of study participation to consent the patient and conduct/collect the study participant questionnaires.

The clinical outcomes and scores, ie characterisation of wound and SINBAD (both part of standard clinical practice), plus ulcer size and PUSH score are conducted by the treating podiatrist. Furthermore, microbiological swabbing of the wound is also performed by the podiatrist.

The patient-reported scores, wound-related quality of life score (Cardiff wound index), generic quality of life score (EQ-5D-5L) and end-of-trial experience survey (Natrox wearers only) are all competed by the patient and the researcher can support the patient if they indicate that they require some assistance (the researcher will not prompt patients to select a certain answer).

[#] Up to 2 weeks early or late

[~]Up to 3 weeks early or late (in exceptional circumstances, wk 9 and 12 visit can be combined if wk 9 visit is late and wk 12 visit can only take place early)

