3.2 Medical Device management and staff training

The Natrox devices and related oxygen delivery systems will be stored in the podiatry clinic rooms or R&D office at the temperature and conditions recommended by the manufacturer. No requirement for involvement pharmacy or clinical trials pharmacist. Standard available stocks of dressings to be used as part of standard foot ulcer care.

The Natrox medical device will be managed as such:

- The suitably trained/delegated podiatrist will apply the Natrox device to the wound. This means both the 'web', the 'tubing' and the oxygen generating 'box'.
- Then the regular dressings will be applied, again by podiatrist (as per usual care)
- At the first study appointment, week 0, the patient will be explained how the box can be detached from the tubing/web, in order to allow patient to wash or change clothes.
- At this point, the patient must also be told to change the box every 24 hrs. The official Natrox instruction leaflet will be given to patient as an aide memoire.
- Patients must be seen in podiatry at least once every 7 days whilst they are in the trial, since the same web should not be on for longer than 7 days. This timing is in line with standard care.
- The web and tubing is replaced at this point. The replacement can take place sooner than after 7 days, if the dressing needs to be changed at that point anyway. Again, the podiatrist changes the web and tubing.
- At each clinic visit the patient is asked if they've experienced any issues with the device.

A team of podiatrists at both recruitment sites have been identified, see protocol summary pages 2-4, and they will be trained on the application and use of the Natrox device by a representative from Inotec AMD Limited. This person will also be available for any troubleshooting once the study is live. The podiatrists and research staff will also attend a site initiation visit on the ANODE study itself. For both sessions an attendance list will be circulated and signed by attending staff. All trained staff will then be added to delegation log for the ANODE study and be delegated the appropriate and relevant tasks in relation to study delivery.

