5.6 Outcome measures

5.6.1 **Primary outcome measures**

To assess the feasibility of conducting a full CRT in the future, the primary outcome measures are mainly:

Trial-related outcome measures

- Participants' compliance to and satisfaction with Natrox device
- Recruitment and attrition rates, willingness of patients to be consented and randomised, response rates to questionnaires, and degrees of missing data
- Testing of eligibility criteria and ability/willingness of clinical staff to partake in recruitment of participants
- Ability of sites and clinicians to recruit and randomise patients
- To assess any training requirements
- Adequacy of duration of follow-up (e.g. in relation to foot ulcer healing)
- Fitness for purpose of data collection methods including across and between care settings
- Suitability of inclusion/exclusion criteria and outcome measure tools.
- Adverse events

5.6.2 **Secondary outcome measures**

This study also aims to record wound characteristics and patient-related outcomes measures, as well as safety endpoints and microbiology assessments.

The main clinical outcome for this trial will be the efficacy of the Natrox oxygen therapy in terms of wound healing. For all participants, wound healing will be measured

Foot ulcer size, measured with wound grid tool (week -4, 0, 3, 6, 9, 12). Measured in % change in cm² - between week 0 and weeks, 3, 6, 9, and 12 respectively

Assessment wound size and characteristics (wk 0,3,6,9,12)

- Clinical characterisation of wound (incl. erythema, purulence, odour), wound closure status
- PUSH and, if applicable, SINBAD DFU score

Extended safety outcome measures, general and in relation to applied Natrox (ongoing):

- Wound infection incidence
- Need for secondary interventions (incl. need for surgery, admission to hospital, iv antibiotics)
- (indirect) reaction to Natrox, the web itself or oxygen therapy
- Any other adverse events

Patient-reported outcome measures (wk 0, 6, 12)

- Quality of life score (EQ-5D-5L and Cardiff Wound Impact Questionnaire)

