8.3 Secondary outcome statistics

The clinically-related objective for this trial is the healing rate of the foot ulcers, as assessed by tracing the wound using a Coloplast measuring grid, or an equivalent performance-equal measuring tool.

The average difference between time points and baseline (week 0) will be calculated per group, 12 weeks being the primary endpoint but weeks 3, 6 and 9 will also be analysed. To compare the groups, the Mann-Whitney U-test will be applied (data will be tested for normal distribution and if applicable, t-test will be applied).

The average change in healing at 12 weeks between the Natrox cohort and the control cohort within the study will be compared using the Mann-Whitney U-test or, if data normally distributed, t-test. Application of this analysis will depend on sample size of control cohort.

The average baseline demographics for participants in each group (Natrox and control) will be described and compared to ascertain the distribution of participants' data for: sex, age, HbA1c level, baseline wound size (cm2), PUSH score, SINBAD DFU grading score (if applicable), EQ5-5D-5L score, CWIQ score, duration of wound (weeks), neuropathy status, ischaemia status.

Other clinical parameters will be recorded too, since they are known to be significantly associated with non-healing of foot ulcers: diabetes status, peripheral arterial disease, heart failure, pretibial oedema (Prompers et al, 2008)

The Chi-squared test will be applied to the above cross-tabulation to determine if there is a significant difference in distribution of treatment outcome in terms of 'status wound healed' (Natrox vs control).

To evaluate the wider effects of the Natrox topical oxygen therapy regime on foot ulcer healing, the following parameters will be compared (median difference between week 0 and different follow-up time points):

- PUSH score
- SINBAD grading score
- Visual analogue pain score
- EQ5-5D-5L score
- CWIQ score

To compare, Mann-Whitney U-test between cohorts, since data is ordinal.

The sample size in this feasibility trial is too small to conduct Cox proportional hazards regression analysis to investigate the role of the dressing regime choice and other in wound healing rates.

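### The week-12 wound measurement may be taken from week 9 to week 15 and overlaps the week-9 window; this blurs the main healing estimate and would bias it if visit timing differed by arm

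*Protocol*

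**What the plan says.** Healing is defined in section 5.6.2 as "Measured in % change in cm² - between week 0 and weeks, 3, 6, 9, and 12 respectively". Section 8.3 compares the arms at each of these weeks, with "12 weeks being the primary endpoint but weeks 3, 6 and 9 will also be analysed". The test is a Mann-Whitney U-test, or a t-test if the data look normal, and no use of actual measurement dates is stated.

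The visit windows are in the footnotes to Table 2 (section 5.4):

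- weeks 0, 3 and 6: "Up to 1 week early or late"
- week 9: "Up to 2 weeks early or late"
- week 12: "Up to 3 weeks early or late"

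The week-12 footnote adds that "wk 9 and 12 visit can be combined if wk 9 visit is late and wk 12 visit can only take place early", and it restricts this to exceptional circumstances.

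Two other passages bear on the point. Section 5.5 splits the 16 weeks of participation so that "4 weeks are screening and 12 weeks are intervention or control". Section 3.2 states: "Patients must be seen in podiatry at least once every 7 days whilst they are in the trial". Section 5.5 also says that the treating podiatrist measures the ulcer, while the researcher attends the study weeks for consent and questionnaires.

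**The concern.** The widest window sits on the most important time point for healing: three times the width used at weeks 0, 3 and 6. Ulcer area changes with time, so a value labelled week 12 but taken between week 9 and week 15 mixes healing with the date of the visit. The windows for weeks 9 and 12 share weeks 9 to 11, so two measurements with different labels can come from the same elapsed time, and a combined visit gives one measurement for two analyses. A visit after week 12 also lies beyond the 12-week intervention or control period, and the protocol does not say how such a value counts.

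The stakes follow from the trial's own purpose. Section 6.1 wants it to inform an effect size and the variance of healing for a larger trial, and section 5.6.1 lists the adequacy of the follow-up duration among the primary feasibility outcomes. Loose timing blurs all three. The trial is also open (section 6.1.1), so a difference in visit timing between arms cannot be ruled out, and that would bias the comparison.

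**Working it through.** **Windows.** Week 12: 12 − 3 = 9 to 12 + 3 = 15. Week 9: 9 − 2 = 7 to 9 + 2 = 11. Shared: weeks 9 to 11. The protocol does not say whether week 12 is counted from the actual or the planned week-0 visit. If from the planned one, the ±1 week at week 0 widens elapsed time to 8 to 16 weeks.

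**Healing rate (assumption).** The only area figures are from the 10-patient device pilot: mean 51% healed at week 8 (section 6.1) and median 53% (section 2). Assume a constant proportional rate, healed(t) = 1 − exp(−kt).

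- From 51%: k = −ln(0.49)/8 = 0.0892 per week. Healed at weeks 9, 12 and 15: 55.2%, 65.7% and 73.8%, a spread of 18.6 points.
- From 53%: k = −ln(0.47)/8 = 0.0944 per week. Healed: 57.2%, 67.8% and 75.7%, a spread of 18.5 points.
- Straight-line healing is an upper variant: 51/8 = 6.4 points per week, 38.2 over six weeks. It implies 95.6% mean healing by week 15, which fits poorly with the closure rates in section 2.

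These spreads describe one patient measured at either end of the window.

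**Complete closure.** Section 2 gives 24% by week 12 on standard treatment, and about 10% for ulcers that had not halved by week 4. With the same formula, 24% gives 18.6% at week 9 and 29.0% at week 15 (10.4 points). The 10% figure gives 7.6% and 12.3% (4.7 points). Those figures count from the start of treatment, not from randomisation, so they are a guide only.

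**Between-arm bias.** For a mean timing gap of g weeks centred on week 12, the shift is healed(12 + g/2) − healed(12 − g/2). With k = 0.0892:

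| Gap (weeks) | Shift (points) |
|---|---|
| 1 | 3.1 |
| 2 | 6.1 |
| 3 | 9.2 |
| 6 | 18.6 |

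A gap of 6 weeks needs every patient in one arm at week 9 and every patient in the other at week 15.

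**Noise when timing is unrelated to arm.** A simulation with 12 per arm and visits uniform over weeks 9 to 15 gives zero bias, a timing SD of 5.3 points, and an arm difference that varies by about ±4.3 points (95%). For assumed SDs of 20, 30 and 40 points, the total SD becomes 20.7, 30.5 and 40.4.

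**Scale.** The difference detectable with 12 per arm at 80% power and two-sided 5% (normal approximation) is (1.96 + 0.84) × SD × √(2/12), or about 1.144 × SD: 22.9, 34.3 and 45.7 points for those SDs.

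**Comparison with a treatment effect (assumption; none is stated).** If controls healed 20%, 30%, 35%, 40% or 45% by week 8, the week-12 difference from the 51% curve would be 37.3, 24.3, 18.1, 12.2 or 6.5 points.

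**The case against.** The case for leaving the window alone is fair. This is a feasibility trial with healing as a secondary outcome, and wide windows are a practical choice. Schedule and windows are the same in both arms, and no mechanism for a timing difference is documented. Even with visits spread evenly over six weeks, the SD rises by only about 1 to 3.5%. The pilot had no screening phase, whereas this trial randomises only ulcers that healed by less than 50% in four weeks, so the rate used above is probably too fast. Combined visits are meant to be exceptional. A separate analysis plan could use actual dates. The seven-day rule is there for replacing the web, and Table 2 schedules ulcer area at the study weeks only.

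Most of this stands, and it limits the size of the point. It does not remove it. The window is fixed in the protocol, and no analysis rule can recover an area that was never measured near week 12. Patients are in clinic weekly in any case, with the person who measures the ulcer.

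A reader might infer from the 18.6-point spread that timing alone could imitate a treatment effect. The documents do not support that. Section 6.1 says there are too few data to gauge the effect. The spread is within one patient, and it reaches the assumed effects above only if controls healed about 35% or more by week 8. As a difference between arms it would need timing to split completely by arm.

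**Conclusion.** The point holds as a modest, avoidable weakness. The main healing time point has a six-week window that overlaps the previous time point, and the protocol still treats the two as separate. With timing unrelated to arm, the cost is noise: about 5 points of added SD in the harsh case of evenly spread visits, and no bias. With a timing difference between arms, the bias is about 3 points per week, so 3 to 6 points for gaps of 1 to 2 weeks. These figures rest on the pilot's 8-week rate continuing unchanged to week 15. In the slower healers randomised here they are probably smaller. Nothing here threatens the primary feasibility objective, but the change is cheap enough to be worth making.

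**What to change.** - In both arms, take wound area and closure status at the routine podiatry visit nearest day 84 (day 63 for week 9), with a target of ±7 days as at weeks 0, 3 and 6. State that days count from the actual week-0 measurement. The targets become weeks 8-10 and 11-13, which do not overlap. At the pilot's rate the spread across the week-12 window falls from 18.6 to 6.1 points, and the timing SD from 5.3 to 1.8.
- Keep the present wide window for the questionnaires.
- If no visit falls within ±7 days, use the nearest measurement in the existing window, flag it, and repeat the week-12 comparison without the flagged values. With only 12 per arm, values should not simply be deleted.
- Count a combined visit once, as week 12 if no other week-12 measurement exists.
- Report the actual day of measurement by arm.

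Cost: a change to the Table 2 footnotes and one analysis rule. The podiatrist may have to measure at a routine visit that the researcher does not attend, and a few week-9 values may become missing.

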5.6 Outcome measures

5.6.1 **Primary outcome measures**

To assess the feasibility of conducting a full CRT in the future, the primary outcome measures are mainly:

Trial-related outcome measures

- Participants' compliance to and satisfaction with Natrox device
- Recruitment and attrition rates, willingness of patients to be consented and randomised, response rates to questionnaires, and degrees of missing data
- Testing of eligibility criteria and ability/willingness of clinical staff to partake in recruitment of participants
- Ability of sites and clinicians to recruit and randomise patients
- To assess any training requirements
- Adequacy of duration of follow-up (e.g. in relation to foot ulcer healing)
- Fitness for purpose of data collection methods including across and between care settings
- Suitability of inclusion/exclusion criteria and outcome measure tools.
- Adverse events

5.6.2 **Secondary outcome measures**

This study also aims to record wound characteristics and patient-related outcomes measures, as well as safety endpoints and microbiology assessments.

The main clinical outcome for this trial will be the efficacy of the Natrox oxygen therapy in terms of wound healing. For all participants, wound healing will be measured

Foot ulcer size, measured with wound grid tool (week -4, 0, 3, 6, 9, 12). Measured in % change in cm² - between week 0 and weeks, 3, 6, 9, and 12 respectively

Assessment wound size and characteristics (wk 0,3,6,9,12)

- Clinical characterisation of wound (incl. erythema, purulence, odour), wound closure status
- PUSH and, if applicable, SINBAD DFU score

Extended safety outcome measures, general and in relation to applied Natrox (ongoing):

- Wound infection incidence
- Need for secondary interventions (incl. need for surgery, admission to hospital, iv antibiotics)
- (indirect) reaction to Natrox, the web itself or oxygen therapy
- Any other adverse events

Patient-reported outcome measures (wk 0, 6, 12)

- Quality of life score (EQ-5D-5L and Cardiff Wound Impact Questionnaire)

6. SUBJECTS

6.1 Anticipated number of research subjects

This concerns a feasibility trial, and therefore the results from this study should inform a potential effect size for Natrox oxygen therapy, and also the degree in variance in wound healing rates (primary clinical outcome). To date, there is not sufficient published data to gain an insight in the effect that Natrox may have on foot ulcer healing. Hayes et al (2017) previously conducted a pilot study involving 10 DFU patients. In that study, there was no screening phase and Natrox treatment lasted for eight weeks. At the week 8 time point, a mean healing vs baseline of 51% was achieved.

Guidance from a publication by Julious (2005) advises the use of 12 participants per treatment arm, and this approach will be taken here (see Table 3). Patient withdrawal rates before week 12 are not known at present and measuring this will be a primary aim

Table 3, sample size numbers required, based on hypothetical differences between published data and study outcomes

	Standard (control) arm	care	Standard care plus Natrox oxygen therapy arm
Patients (n)	12		12

Since this concerns a randomised controlled trial, albeit in the shape of a feasibility study, reprting will be done in line with CONSORT guidelines (Schulz, Altman & Moher 2010). The number of patients screened but who did not meet the inclusion criteria or who declined to participate will be recorded, as will any patients who are lost to follow-up (Appendix 2).

Since this study involves a screening period, after which patients may not qualify for Natrox intervention, it is anticipated that more than 20 patients will be recruited. The patient attrition rate (withdrawal and loss to follow-up) will also be recorded, since this involves a study with at multiple visits, albeit incorporated into standard clinical appointments. Patients will be recruited from the adult (age 18+) population routinely seen by the evaluating clinical staff members.

6.1.1 Randomisation

Following written consent at -4 weeks, participants will be observed for four weeks to establish healing rate. At the end of four weeks, patients are only eligible for the intervention phase if their wound has healed <50% in the preceding four weeks. At this point, week 0, participants are allocated at random to the control or Natrox intervention group, using a randomised sequence from the freeware randomisation programme, see https://www.randomizer.org/. The randomisation is stratified for ulcer size, with PUSH score of 5 or less, and 6 or above as the cut-off. This size has been determined as the average size of a presenting foot ulcer previously (Zimny et al, 2002).

Sequential envelopes with each next randomisation allocation will be used to achieve concealment and these will be kept in the research department. The researcher will then inform the regular healthcare professional for the participant in question, and the participant themselves, which treatment they've been allocated to. The researcher will dispatch a Natrox device to the clinic where the participant will be seen. At this stage the continuous Natrox treatment (though disconnection for washing or changing of clothes is allowed) will commence.

As the study involves administration of a visible device, it is not possible to achieve blinding for the participants nor the researchers – it is recognised that this increases the risk of bias. Since the device has an indicator to show it is functioning, applying a sham device is not possible either on this occasion.

